STUDY PROTOCOL

1. Study Title

Levetiracetam Versus Phenobarbitone for the Treatment of Neonatal Seizures in a Tertiary Care Hospital

Short title/acronyms: Levetiracetam Versus Phenobarbitone for the Treatment of Neonatal Seizures

2. Protocol ID

DHQ-DIK-IWEB NO. 4806

Date: 26 February 2024.

ClinicalTrials.gov Identifier: NCT Not Yet Assigned

3. Background & Rationale

Neonatal seizures are the most common neurological emergency in neonates and are associated with significant morbidity and mortality. Phenobarbitone has traditionally been the first-line anticonvulsant; however, its efficacy is limited and it has significant adverse effects. Levetiracetam is emerging as a safer alternative with promising seizure control rates. This study aims to compare the efficacy and safety of levetiracetam versus phenobarbitone in neonates with seizures.

4. Objectives

Primary Objective

To compare seizure control rates within 24 hours between levetiracetam and phenobarbitone in neonates with clinically diagnosed seizures.

Secondary Objectives

- To compare time to seizure cessation between both drugs.
- To compare the need for second-line anticonvulsant therapy.
- To compare seizure recurrence during hospital stay.
- To compare adverse drug reactions.
- To compare mortality rates.

5. Study Design

A prospective randomized controlled trial conducted at the Neonatal Intensive Care Unit (NICU) and Pediatric wards of a tertiary care hospital.

6. Study Setting

Neonatal Intensive Care Unit (NICU) and Pediatric ward at [Your Hospital Name], Pakistan.

7. Study Population

Neonates (0–28 days) with clinically diagnosed seizures admitted to NICU or Pediatric ward.

8. Sample Size

Based on previous literature, assuming seizure control rates of 70% with levetiracetam and 50% with phenobarbitone, with 80% power and 5% significance level, the calculated sample size is **n = 100 (50 in each group)**. However we will include all the patients accepting the inclusion criteria during one year of study.

9. Inclusion Criteria

- Neonates (0–28 days old) with clinically diagnosed seizures.
- Term and preterm neonates.
- Parents/legal guardians provide informed consent.

10. Exclusion Criteria

- Major congenital anomalies or genetic syndromes.
- Severe renal or hepatic impairment.
- Neonates already receiving anticonvulsants before admission.
- Neonates with metabolic seizures not responding after correction.

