- Neonates with CNS infection requiring specific treatment (unless seizures persist).
- Parents refuse consent.

11. Intervention

Arm A: Levetiracetam

- Loading dose: 20 mg/kg IV
- Repeat dose: 20 mg/kg IV after 12 hours if seizures persist
- Maintenance dose: 10 mg/kg IV/PO twice daily until seizure control or discharge

Arm B: Phenobarbitone

- Loading dose: 20 mg/kg IV
- Repeat dose: 10 mg/kg IV after 20 minutes if seizures persist
- Maintenance dose: 5 mg/kg IV/PO once daily until seizure control or discharge

12. Outcome Measures

Primary Outcome

Seizure control rate within 24 hours after first-line treatment.

Secondary Outcomes

- Time to seizure cessation
- Need for second-line anticonvulsant
- Seizure recurrence during hospital stays
- Adverse drug reactions
- Mortality during hospital stay

13. Study Procedures

1. Neonates with clinical seizures will be assessed by pediatric/neonatology team.
2. Eligible neonates will be randomized into either levetiracetam or phenobarbitone group.
3. Baseline data including demographic details, gestational age, birth weight, and clinical status will be recorded.
4. Standard investigations will be done (CBC, blood glucose, electrolytes, ABG, neuroimaging if required).
5. Treatment will be administered as per group allocation.
6. Monitoring of seizure activity and side effects will be done for 72 hours and until discharge.
7. Data will be recorded on a structured proforma.

14. Randomization

Simple randomization using Lottery method.

15. Data Collection

Data will be collected on a structured proforma and entered into SPSS version 25.

16. Ethical Considerations

Approval will be obtained from the Institutional Review Board (IRB). Informed consent will be obtained from parents/legal guardians.

17. Principal Investigator:

[name]

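### Treatment is assigned by a manual lottery with no concealment, independent allocator or allocation log described, in a trial that states no masking

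*Protocol*

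**What the plan says.** Protocol Section 14 (Randomization) is a single line: "Simple randomization using Lottery method". Section 13 adds the order of events. Step 1 is "Neonates with clinical seizures will be assessed by pediatric/neonatology team" and step 2 is "Eligible neonates will be randomized into either levetiracetam or phenobarbitone group"; baseline data follow at step 3 and investigations at step 4. Consent is an inclusion criterion (Section 9).

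Section 5 describes the design as "A prospective randomized controlled trial conducted at the Neonatal Intensive Care Unit (NICU) and Pediatric wards of a tertiary care hospital", with no word on masking. Section 11 gives different schedules: for levetiracetam, "Repeat dose: 20 mg/kg IV after 12 hours if seizures persist"; for phenobarbitone, "Repeat dose: 10 mg/kg IV after 20 minutes if seizures persist". Maintenance is twice daily in one arm and once daily in the other.

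Section 8 plans 50 neonates per group and then opens the total: "However we will include all the patients accepting the inclusion criteria during one year of study".

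The SAP tests the primary outcome with an unadjusted chi-square or Fisher's exact test. Gestation, birth weight and etiology appear there only as optional subgroups.

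**The concern.** Randomization protects the comparison only if the person enrolling a neonate can neither foresee nor alter the next assignment. A manual lottery can be run that way, but the plan names no feature that would make it so: no one separate from the enrolling team, no sealed or numbered lots, no record of draws.

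Three features raise the stakes.

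- Without stated masking, and with schedules that reveal the arm, nothing later in the trial would make up for a weakness at allocation.
- Seizures are diagnosed clinically at entry, and no masked assessor is named for seizure control at 24 hours.
- The protocol's background section presents levetiracetam as the safer emerging option, so a preference among staff is plausible.

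If neonates with a better outlook go preferentially to one arm, the primary comparison is biased. Adjustment can remove only the part carried by recorded factors.

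**Working it through.** **What is and is not specified.** Both documents were searched for each element.

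| Element | Protocol | SAP |
|---|---|---|
| Type of randomization | Simple, by lottery (Section 14) | Not stated |
| Who prepares, holds or draws the lots | Not stated | Not stated |
| Place and time of the draw | After assessment (Section 13); place not stated | Not stated |
| Concealment of the next assignment | Not stated | Not stated |
| Allocation log | Not stated | Not stated |
| Masking of carers, parents or assessors | Not stated | Not stated |
| Stratification or covariate adjustment | Not stated | Not stated (optional subgroups only) |

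**Illustration of steering.** The assumptions are not in the documents: no true drug effect; half the neonates have a good prognosis (80% controlled at 24 hours) and half a poor one (40%); for a fraction f of neonates the arm is chosen, good prognosis to levetiracetam (A) and poor to phenobarbitone (B); the rest are drawn fairly.

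- Good-prognosis share of all neonates in A: 0.5 × [(1 − f)/2 + f] = 0.25(1 + f). Poor-prognosis share in A: 0.25(1 − f). Arm A holds 0.5 of the total.
- Control rate in A: [0.25(1 + f) × 0.8 + 0.25(1 − f) × 0.4] / 0.5 = 0.6 + 0.2f. In B: 0.6 − 0.2f. False difference: 0.4f.
- Check at f = 0.10 with 50 per arm: A = (45 × 0.6 + 5 × 0.8)/50 = 62%; B = (45 × 0.6 + 5 × 0.4)/50 = 58%.
- Type I error (normal approximation): SE = √[(0.62 × 0.38 + 0.58 × 0.42)/50] = 0.0979; shift = 0.04/0.0979 = 0.409; rejection probability = 1 − Φ(1.96 − 0.409) + Φ(−1.96 − 0.409) = 0.069.

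| Neonates steered (of 100) | Rates A vs B | False difference | Two-sided type I error |
|---|---|---|---|
| 5 | 61% vs 59% | 2 points | 5.5% |
| 10 | 62% vs 58% | 4 points | 6.9% |
| 20 | 64% vs 56% | 8 points | 13.0% |

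An exact binomial calculation for 10 steered neonates (45 at 60% and 5 at 80% or 40% in each arm) gives 7.0%, against 5.2% for the same test without steering. The planned difference is 70% − 50% = 20 points.

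**How much the lack of blocking matters.** Under simple randomization of 100, the chance of an exact 50:50 split is 8.0%, and of 60:40 or worse 5.7% (Binomial(100, 0.5)). The effect on power for 70% vs 50%, two-sided 5%, is small.

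- Exactly 50 per arm: Φ{[0.2 − 1.96 × √(2 × 0.6 × 0.4/50)] / √[(0.7 × 0.3 + 0.5 × 0.5)/50]} = Φ(0.083) = 53.3%.
- Averaged over simple randomization of 100: 52.9%, a loss of 0.4 points.
- At 60:40: 51.0% to 52.3%, depending on which arm is larger.

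(That 53.3% falls short of the 80% claimed in Section 8 is a separate matter of sample size.)

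**Baseline balance.** In simulations at N = 100, the share with a baseline factor differed between arms by 15 points or more as follows (prevalence assumed):

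| Prevalence | Simple | Equal arms, unstratified |
|---|---|---|
| 20% | 6.3% | 6.0% |
| 30% | 10.3% | 10.1% |
| 50% | 13.5% | 13.4% |

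Blocking without stratification therefore does not correct such imbalance; stratification or adjustment is needed.

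**The case against.** The strongest reply is that silence is not evidence of a fault. A lottery can be concealed: lots may be sealed, drawn by someone outside the team, or drawn in advance to build a list. A reader might infer that the draw is open, made at the bedside and in the hands of the recruiting clinician. The documents do not support that. The NICU and wards are named as the trial setting, not as the place of the draw. Section 13 also puts assessment before randomization, and consent is required for entry, so allocation is meant to come after both. That order deserves credit, but it does not hide the next assignment, and nothing requires consent and eligibility to be recorded before the draw.

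A reader might also infer a box of 50 + 50 slips that becomes predictable or runs out under uncapped enrolment. No such box is described, and drawing with replacement would never run out. What stands is that the protocol does not say which kind of lottery it means.

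Simple randomization is itself valid and makes the next assignment unpredictable when properly done; small fixed blocks in an unmasked trial could make it more predictable. Chance imbalance is not bias, is already allowed for in the test's error rate, and on recorded factors can be handled by adjustment. All of this stands, so blocking and unequal arm sizes are side remarks.

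Finally, the steering rates and prognoses above are invented for illustration. That is true, and they show scale only.

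**Conclusion.** The point holds as a gap in protection, not as a demonstrated breach. With a manual lottery, no concealment, no independent allocator, no log, no stated masking and visibly different schedules, nothing in the plan prevents the enrolling team from influencing allocation, and a reader cannot verify that it did not happen. Steering on unmeasured prognosis could not be repaired in analysis.

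The size is unknown. Under the assumed 80%/40% prognoses, steering 5 to 20 of 100 neonates would produce false differences of 2 to 8 points and type I error between about 5.5% and 13%; at 10 neonates, about 4 points and 7%. The change should be made, and it is cheap. The stronger conclusion that allocation was in fact open or manipulated is not supported.

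**What to change.** **Replace Section 14 with text to this effect:** allocation follows a computer-generated list, long enough for the full enrolment year, prepared by an existing hospital employee who does not enrol patients (for example in pharmacy). Allocations are kept in sequentially numbered, opaque, sealed envelopes. Each is opened only after consent and eligibility are recorded and the neonate's study number is written on it. Every opening is entered in an allocation log. If blocks are used, their size varies at random and they are stratified by term/preterm.

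**In the SAP:** adjust the primary analysis for term/preterm, derived from the gestational age already recorded at baseline.

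**If enrolment is complete** (the SAP gives primary completion as March 31 2025): report how the lottery was run and by whom, and present the term/preterm-adjusted primary analysis.

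**Cost:** one protocol paragraph, one SAP sentence, and a one-off list and set of envelopes made by existing staff. The downside is that envelopes must be prepared and accounted for. No extra patients, procedures or data items are needed.

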STATISTICAL ANALYSIS PLAN (SAP)

Study: Levetiracetam Versus Phenobarbitone for the Treatment of Neonatal Seizures in a
Tertiary Care Hospital

Principal Investigator: [name]

Official Study Title:

**Levetiracetam Versus Phenobarbitone for the Treatment of Neonatal Seizures in a
Tertiary Care Hospital**

Short title/acronyms: **Levetiracetam Versus Phenobarbitone for the Treatment of Neonatal
Seizures**

ClinicalTrials.gov Identifier:

NCT Not Yet Assigned

Organization's Unique Protocol ID:

DHQ-DIK-IREB NO. 4806

Document Type:

Statistical Analysis Plan (SAP)

Date:

Study Start Date

April 08 2024

Primary Completion Date

March 31 2025

Study Completion Date

April 10 2025

Prepared By:

[name]

Analysis Population

- **All randomized neonates** (Intention-to-Treat, ITT)
- **Per-protocol population** for sensitivity analysis (neonates who completed treatment as per protocol)

Descriptive Statistics

- **Continuous variables:** mean \pm SD or median (IQR)
- **Categorical variables:** frequency (%)

Outcome Analysis

Primary Outcome:

- Seizure control rate within 24 hours
 - **Compare** seizure control between levetiracetam and phenobarbitone groups
 - **Statistical Test:** Chi-square or Fisher's exact test
 - **Significance level:** $\alpha = 0.05$

Secondary Outcome Analysis

- **Time to seizure cessation**
 - Independent t-test or Mann–Whitney U test
- **Need for second-line anticonvulsant**
 - Chi-square test
- **Seizure recurrence during hospital stay**
 - Chi-square test
- **Adverse drug reactions**
 - Chi-square test
- **Mortality during hospital stay**
 - Chi-square test

Subgroup Analysis (optional)

- Preterm vs Term neonates
- Birth weight <2500 g vs ≥ 2500 g
- Etiology of seizures (HIE vs metabolic vs infection vs others)

Handling Missing Data

- **Multiple imputation** if missing data $> 5\%$
- **Sensitivity analysis** comparing complete case vs imputed dataset

Software

- Analysis performed using **SPSS version 23**,

Reporting

- **Two-sided p-values**
- **95% confidence intervals** for effect estimates
- **Tables and figures** for primary and secondary outcomes

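### Time to seizure cessation is compared by t-test or Mann-Whitney with no horizon and no rule for neonates who do not stop, die first, or stop only after a second-line drug

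*SAP*

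**What the plan says.** Protocol section 4 lists the objective "To compare time to seizure cessation between both drugs", and section 12 repeats it as a secondary outcome, by name only. The SAP (Secondary Outcome Analysis) gives one line for it: "Independent t-test or Mann–Whitney U test". The SAP's main population is "All randomized neonates (Intention-to-Treat, ITT)". Under Handling Missing Data it plans "Multiple imputation if missing data" exceed 5%, with a sensitivity comparison against complete cases.

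Other parts of the Protocol bear on the outcome without being linked to it:

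- Section 11 has maintenance in both arms run "until seizure control or discharge".
- Section 12 lists "Need for second-line anticonvulsant" and "Mortality during hospital stay" as separate outcomes.
- Section 13 states: "Monitoring of seizure activity and side effects will be done for 72 hours and until discharge".

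The only outcome with a window in hours is the primary, at 24 h.

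**The concern.** A t-test needs a number for each neonate, and a Mann-Whitney test needs a rank. A neonate still seizing when observation ends, or who dies first, has no stopping time. The Protocol allows for such neonates: section 11 lets discharge come before control, and in-hospital death is an outcome. A neonate who stops after a second-line drug does have a time, but the plan does not say whether it counts for the randomised drug.

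With no rule for this outcome, the analyst is left with the general missing-data rule. At 5% or less missing, that rule gives no instruction, and leaving these neonates out is the easy default; the complete-case check also leaves them out. Above 5%, it imputes a time for an event that did not happen. Leaving them out selects on the outcome being compared, because those removed are the failures. At stake are the size, and possibly the direction, of the result on a stated secondary objective, and a choice that could be made after the data are seen.

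**Working it through.** **The plan's own figure.** There is none for this outcome. The sample size in Protocol section 8 concerns seizure control and is not needed for this point. It supplies only the inputs below.

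**Inputs.** From Protocol section 8: 70% vs 50% controlled, 50 per arm, 5% level. From the SAP: two-sided tests and the 5% missing-data trigger. Assumed, because the documents are silent: the 70% and 50% apply at 24 h, the time distribution, the horizon, and the rescue and death rates.

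**Step 1: hazards.** With constant hazards, levetiracetam −ln(0.3)/24 = 0.05017 per hour and phenobarbitone −ln(0.5)/24 = 0.02888 per hour.

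**Step 2: share with no stopping time, no rescue or death.**

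- 72 h: 0.3³ = 2.7% and 0.5³ = 12.5%, pooled (2.7 + 12.5)/2 = 7.6%, above the 5% trigger.
- 96 h: 0.3⁴ = 0.8% and 0.5⁴ = 6.3%, pooled 3.5%, below it.
- 168 h: 0.3⁷ = 0.02% and 0.5⁷ = 0.8%.

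**Step 3: means to 72 h.** The restricted mean in all randomised is (1 − S)/hazard, where S is the share not stopped by 72 h: 0.973/0.05017 = 19.4 h and 0.875/0.02888 = 30.3 h, a difference of 10.9 h. The mean in stoppers is (restricted mean − 72·S)/(1 − S): (19.4 − 1.94)/0.973 = 17.9 h and (30.3 − 9.0)/0.875 = 24.3 h, a difference of 6.4 h.

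**Step 4: simulated power, 50 per arm, 4000 trials (error about 1 point), no rescue or death.**

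| Horizon | Stoppers only, Mann-Whitney | Stoppers only, t-test | All, worst-rank Mann-Whitney | All, log-rank |
|---|---|---|---|---|
| 72 h | 38% | 43% | 64% | 75% |
| 96 h | 51% | 57% | 66% | 77% |
| 120 h | 57% | 65% | 65% | 77% |
| 168 h | 63% | 74% | 65% | 77% |

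**Step 5: sensitivity of the loss (Mann-Whitney, stoppers only vs worst rank).**

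- *Hazard shape.* Weibull times with the same 24 h rates. Falling hazard (shape 0.7): 24% vs 65% at 72 h and 49% vs 65% at 168 h. Rising hazard (shape 1.5): 59% vs 66% and 64% vs 64%.
- *Rescue.* Everyone uncontrolled at 24 h is rescued, 60/70/80/90% of them stop within the next 24 h in both arms, and observed times count. At 72 h: 48 vs 51%, 47 vs 50%, 49 vs 49% and 53 vs 53%, a loss of 0 to 3 points, and nil at 168 h. A second set of runs (4000 trials), with stopping after rescue at a constant rate, gave 0 to 4 points. This depends on late stoppers continuing to stop. If those not stopped within 24 h of rescue never stop, the 72 h figures are about 39 vs 51%, 43 vs 52%, 47 vs 52% and 49 vs 51%, and a 168 h horizon does not recover the loss.
- *Death.* If 10, 20 or 30% of those uncontrolled at 24 h die then, the 168 h figures are 60 vs 63%, 55 vs 60% and 49 vs 58%.

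**Step 6: direction.** Suppose 70% vs 50% stop within 24 h and stopping times among stoppers are truncated exponential. With the same scale (6 h) in both arms, the stoppers-only tests reject in 4 to 5% of trials, against 51% for log-rank in all. With scales of 9 h (levetiracetam) and 4 h (phenobarbitone), stoppers on levetiracetam average 3.2 h longer, and the stoppers-only tests reject in 60 to 67%, against the arm with more neonates controlled.

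**The case against.** The strongest reply is that the SAP nowhere says a neonate who is still seizing is missing. Its population is all randomised neonates, and an analyst could cap the time or assign a worst rank within the tests named. That stands: a reader might infer that the plan drops failures, but the documents support only that it gives no rule and that its one rule for absent values would mishandle them.

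A reader might also take 38% vs 64% as the trial's expected loss. The documents do not support that either. Section 13 continues monitoring to discharge, so 72 h is not a stated end of observation, and second-line treatment is anticipated. The figure needs both a 72 h cut and no rescue.

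Three further inferences fail:

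- *That omission always shrinks the difference.* Step 6 shows that it can reverse it. The plan's control rates also do not say which arm has more neonates who never stop.
- *That the horizon alone decides whether imputation starts.* With 20% deaths, about 6% and 11% have no value even at 168 h, and the SAP does not say whether its 5% is pooled or per outcome.
- *That keeping everyone always matters more than the test.* At 120 h, worst rank adds 8 points over stoppers only (57% to 65%), and log-rank adds 12 over worst rank (65% to 77%). At 168 h the stoppers-only t-test (74%) beats worst-rank Mann-Whitney (65%).

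Finally, ranking deaths as worst overlaps with the mortality outcome, and counting rescued neonates as failures overlaps with the second-line outcome. Both are fair points about the choice of rule, not reasons to have none.

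**Conclusion.** The concern holds as a missing rule with a real risk of bias. The named tests need a value or rank for every neonate, and neither document ties to this outcome a horizon or a treatment of those who have not stopped, die first, or stop after rescue. Using the missing-data rule would either condition on the outcome, contrary to intention to treat, or invent stopping times. Bias would usually be towards a smaller difference if failures are commoner in one arm, but the direction depends on how fast the stoppers are.

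In the illustration, the Mann-Whitney loss runs from about 26 points (64 − 38, 72 h cut, no rescue or death) to about 2 points at 7 days, and about 0 to 3 points where rescue is largely successful and observed times count. A falling hazard, deaths, or rescue that leaves some neonates never stopping makes it larger than these low values. All of this rests on assumed time distributions and event rates and shows range only. The point concerns one secondary outcome; the primary analysis is not affected. It should be fixed before analysis.

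**What to change.** In the SAP, under this outcome:

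- Analyse all randomised neonates, with the clock from the first loading dose and a stated horizon (for example 72 h, within the Protocol's monitoring window).
- Use Kaplan-Meier and log-rank, with neonates not stopped or dead before cessation counted as not stopped through the horizon. Alternatively keep Mann-Whitney with the worst rank for them, which is simpler but less powerful in the illustration.
- Report the difference in restricted mean time to the horizon with a 95% confidence interval.
- State whether cessation after a second-line drug counts. Under intention to treat, the observed time can count for the randomised arm, with a sensitivity analysis treating rescued neonates as not stopped.
- State that these neonates are not missing and are not imputed. Keep multiple imputation for times that are truly unrecorded.

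The cost is a few sentences in the SAP, and proforma fields for the order and times of cessation, second-line drug and death. The downside is that cessation after the horizon is ignored. The sensitivity analysis answers a narrower question, cessation on the first-line drug alone.
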